7.10 Post-study therapy

After conclusion of the clinical study, patients will receive further medical care as per standard of care and local institution guidelines at the discretion of the treating physician.

8 Procedures and variables

8.1 Description of visits

Any questions regarding the protocol should be directed to the National Coordinating Investigator or the Sponsor's Medical Expert.

All of the protocol required assessments are listed in VII Schedule of assessments and procedures.

All data obtained from these assessments must be recorded in the subject's source documentation. All study visits during the Treatment Period (both primary and extension phases) must occur within 3 days of the scheduled day.

A 5-day window is allowed for the EOT visit. If a subject is discontinued during a regular scheduled visit, all EOT procedures should be completed at that visit.

A window of ± 5 days is allowed for posttreatment FU 1 visit at which the last AE assessment will take place. The subsequent FU 2 visit (=EOS) will take place within ± 14 days of the scheduled date as described in VII Schedule of assessments and procedures.

Serum chemistry laboratory analyses, automated CBC, cytomorphology and cytogenetic analyses will all be performed locally.

Cytomorphology analyses will be carried out locally.

Refer to the eCRF completion guidelines for additional information related to data entry requirements of local laboratories.

Sample collection, processing, storage, and shipment procedures (for translational NGS analyses and study-specific biomaterial collection) will be provided in the Study Laboratory Manual.

8.1.1 Screening ()

A subject information session will be held. Considering site-specific logistic requirements, the investigator may decide upon timing of the screening examinations (e.g., starting immediately

after the informed consent procedure at the earliest; possible split-up into more than one visit). If the (first) screening procedures already start on the same day (same date) as the subject signs the informed consent form, the time of the subject's signature must be recorded in the source documents.

Note: No screening procedures may be performed unless written informed consent has been obtained.

Assessment of inclusion/exclusion criteria for study eligibility

Screening evaluations will be performed for all subjects to determine study eligibility. These evaluations must be completed within [REDACTED] of the first administration of the IMP (refer to VII Schedule of assessments and procedures for further information). Screening laboratory values must demonstrate subject eligibility, but may be repeated within the screening window, if necessary.

Procedures and evaluations to be performed during the screening period are specified in VII Schedule of assessments and procedures and in section 8.2 Descriptions of assessments.

Bone marrow and peripheral blood samples for local assessments

MDS/AML diagnosis confirmation at screening requires both BM, and PB samples. Samples will be reviewed locally.

The screening BM, and PB samples should be collected within the protocol screening window or [REDACTED] prior to the first administration of the IMP. If a subject is rescreened (e.g., due to retesting of another lab), repeat BM samples do not need to be collected contingent the initial samples were adequate for cytomorphology/cytogenetic assessment.

Sample collection, processing and storage should be done as per local standard procedures.

Local cytomorphology assessment

BM and PB samples will be prepared and reviewed locally for analysis to confirm MDS/AML diagnosis and baseline blast percentages as well as WHO classification (Appendix I, section 16.1)) prior to the first administration of the IMP.

Local cytogenetic analysis

Local laboratories will conduct cytogenetic analysis. The local laboratory will provide standardized analysis and reporting for all subjects.

In case a historic record of cytogenetic for the subject (not older than 3 months) is available, these results can be used for the screening visit. But at the latest at [REDACTED] a new analysis must be performed.

Results from local cytogenetic analysis should be used to determine baseline IPSS-R category for MDS patients (Appendix II, section 16.2).

8.1.2 Enrollment for treatment

Patients eligible for study participation will be enrolled by confirmation in the eCRF. Therefore, all assessments between screening and cycle 1 day 1 must be available to check the eligibility criteria. With enrollment, the previously assigned patient number will be used further. For details, please refer to section 6.5.

8.1.3 Treatment period

The subject will start treatment upon confirmation of eligibility. The subject must start treatment within [REDACTED] of signing the ICF. If screening assessments are performed within 72 hours of C1D1, serum chemistry laboratory assessments and physical examinations need not be repeated at C1D1 with the exception of automated CBC.

If subject completed the QoL EORTC QLQ-C30 questionnaire at Screening within 2 weeks of C1D1, it does not have to be repeated at C1D1. If performed on C1D1, it should be completed prior to IMP administration.

On dosing days, local laboratory levels should be assessed prior to each IMP administration to ensure dose modification rules are followed as outlined in section 7.3 Dose modification guidelines.

8.1.4 Primary Phase of the Treatment Period: [REDACTED]

Subjects will receive IMP on [REDACTED] each [REDACTED] treatment cycle.

Treatment cycles are [REDACTED] in duration and will occur as described in section 7.1 Treatment regimen.

After completion of cycle 2, early disease assessments according to the combined MDS/AML response criteria (Appendix III a), section 16.3) will be performed, involving local cytomorphology assessment. If signs of disease progression are present at this assessment, treatment with imetelstat must be discontinued and the patient undergoes EOT.

Procedures/evaluations to be performed during the Primary Phase of the Treatment Period and their frequency are specified in VII Schedule of assessments and procedures and in section 8.2. Descriptions of assessments. The procedures/evaluations should be performed prior to dosing on the visit day, unless otherwise specified.

8.1.5 MDS/AML disease assessment: [REDACTED]

The primary MDS/AML disease assessment according to the combined MDS/AML response criteria (Appendix III a), section 16.3) (primary endpoint assessment) will be performed on samples taken at [REDACTED]. The assessment will be performed by the corresponding investigator.

The disease assessment for the primary endpoint should be completed after four completed cycles with imetelstat (allowing for dose delays). For the disease assessment at least the results of the cytomorphology assessment, automated CBC values and cytogenetic results of visit 9 as well as any information on Hb and transfusions between enrollment and visit 9 are required and must be available prior to / for the disease assessment.

In order for subjects to remain on treatment beyond the first four cycles, the following criteria must be confirmed upon the completion of the disease assessment by the investigator based on the combined response criteria based on IWG 2018 criteria (MDS)¹ and the criteria of the European LeukemiaNet (AML)²:

- **At least partial remission (PR):**
 - This includes CR, CRi, and PR and HI (any line) as per the combined response criteria used in this trial (see Appendix III a))

MLFS will be recorded but is not a criterion for treatment continuation.

Based on the outcome of the disease assessment, subjects will either be discontinued from treatment with IMP and enter the post-treatment follow-up period or continue treatment with IMP in the extension phase of the treatment period.

For subjects that meet the criteria to continue treatment in the extension phase, the duration between the last dose of IMP administered in the primary phase and the first extension phase dose should not be delayed solely due to awaiting cytomorphology/cytogenetics results contingent that the investigator has confirmed absence of signs of disease progression based on review of peripheral blood parameters.

A BM biopsy is to be collected only when adequate aspirate is not attainable or if the BM aspirate shows fewer than 5% bone marrow blasts. Whenever a BM sample is collected, both BM and PB smears are to be prepared. Refer to the Laboratory Manual for additional information.

Further procedures/evaluations to be performed at [REDACTED] are specified in VII Schedule of assessments and procedures, part 1 and in section 8.2 Descriptions of assessments.

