2.3 Study endpoints

2.3.1 Primary endpoint

The primary endpoint of the study is defined as overall hematological response rate as assessed in [REDACTED] of treatment with imetelstat.

All patients with one of the following responses assessed by samples and procedures taken/carried out at [REDACTED] are defined as responders (assessed through the combined response criteria for MDS and AML used in this trial (see Appendix III a), section 16.3):

[1] CR, CRi, PR as defined in Appendix III a)

[2] Hematologic improvement (for one or several lines) as defined in Appendix III a)

Response rate is calculated as follows: number of responders divided by the number of all patients of the analysis set. Patients for whom the overall hematologic response cannot be determined will be considered as treatment failures.

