6.3 Inclusion criteria

Subjects must fulfill all of the following criteria before inclusion in the study:

- 1 Signed written informed consent
- 2 Male and female ≥ 18 years at the first screening
- 3 Must be able to adhere to the study visit schedule and other protocol requirements
- 4 Initial diagnosis of AML or MDS according to WHO 2016 classification
- 5 At least one cytopenia (ANC $< \blacksquare/\mu\text{L}$ or platelet count $< \blacksquare/\mu\text{L}$ or hemoglobin $< \blacksquare \text{ g/dL}$)
- 6
 - a. Failure to achieve complete or partial response or hematological improvement observed after at least six azacitidine monotherapy or four decitabine monotherapy based 4-week treatment cycles administered during the past two years
OR
 - b. Failure to achieve complete or partial response or hematological improvement observed after at least two 4-week treatment cycles with azacitidine plus venetoclax or with decitabine plus venetoclax during the past two years

- OR
- c. Relapse after initial complete or partial response or hematological improvement observed after at least six (azacitidine) or four (decitabine) based 4-week treatment cycles administered during the past two years
- OR
- d. Relapse after initial complete or partial response or hematological improvement observed after at least two 4-week treatment cycles with azacitidine plus venetoclax or with decitabine plus venetoclax during the past two years
- OR
- e. Intolerance to treatment with HMA-based therapy during the past two years
- 7 Not eligible for allogeneic stem cell transplantation
- 8 $\geq 5\%$ bone marrow blasts at screening
- 9 Off all other treatments for AML/MDS for at least 14 days; G-CSF and erythropoietin are allowed before and during the study as clinically indicated
- 10 ECOG performance status of 0-2
- 11 Biochemical laboratory test values must be within the following limits:
[REDACTED]
[REDACTED]
[REDACTED]
[REDACTED]
[REDACTED]
- 12 Availability of blood counts and transfusion events for previous 16 weeks
- 13 Women of childbearing potential and practicing a highly effective method of birth control according to the Clinical Trial Facilitation Coordination Group Recommendation (Version 1.1, 2020):
- combined (estrogen and progestogen containing) hormonal contraception associated with inhibition of ovulation:
 - o oral
 - o intravaginal
 - o transdermal
 - progestogen-only hormonal contraception associated with inhibition of ovulation:
 - o oral
 - o injectable

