16.2 Appendix II: International Prognostic Scoring System Score Revised (IPSS-R)

According to: Greenberg PL, Tuechler H, Schanz J, et al. Revised international prognostic scoring system for myelodysplastic syndromes. Blood 2012;120(12):2454–65.

Points for calculation							
	0	0.5	1	1.5	2	3	4
% blasts in BM	≤ 2	-	> 2 - < 5	-	5 - 10	> 10	-
Karyotype	very good ¹	-	good ²	-	inter-mediate ³	poor ⁴	very poor ⁵
Hemoglobin (g/dl)	≥ 10	-	8 - < 10	< 8	-	-	-
Platelets (/nl)	≥ 100	50 - < 100	< 50	-	-	-	-
Neutrophils (/nl)	≥ 0.8	< 0.8	-	-	-	-	-

Risk Score	
Very low risk	≤ 1.5
Low risk	> 1.5 - 3
Intermediate risk	> 3 - 4.5
High risk	> 4.5 - 6
Very high risk	> 6

For IPSS-R classification you can also use the “MDS Center” App which is available in the Apple Store or Google Play Store.

16.3 Appendix III:

a) Combined response assessment criteria for MDS and AML

Based on IWG 2018 criteria (MDS)¹ and the criteria of the European LeukemiaNet (AML)²

CATEGORY	DEFINITION
Complete remission (CR)	Bone marrow blasts <5%; absence of circulating blasts and blasts with Auer rods; absence of extramedullary disease; ANC $\geq 1.0 \times 10^9/L$ (1000/ μL); platelet count $\geq 100 \times 10^9/L$ (100 000/ μL)
CR with incomplete hematologic recovery (CR _i)	All CR criteria except for residual neutropenia ($<1.0 \times 10^9/L$ [1000/ μL]) or thrombocytopenia ($<100 \times 10^9/L$ [100 000/ μL])
Partial remission (PR)	All hematologic criteria of CR; decrease of bone marrow blast percentage to $\geq 5\%$; and decrease of pretreatment bone marrow blast percentage by at least 50%
Morphologic leukemia-free state (MLFS)	Bone marrow blasts <5%; absence of blasts with Auer rods; absence of extramedullary disease; no hematologic recovery required
Stable disease (SD)	Absence of CR, CR _i , PR, MLFS; and criteria for PD not met

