Platelet response (HI-P) (pretreatment, $< 100 \times 10^9/L$)	
 Absolute increase of $30 \times 10^9/L$ for patients starting with $>20 \times 10^9/L$ PLTs or Increase from $<20 \times 10^9/L$ to $>20 \times 10^9/L$ and by at least 100% 
In addition,
 
 Evolution of bleeding symptoms is to be taken into account Increments of platelets also for patients with a pretreatment PLT count of $>100 \times 10^9/L$ are to be reported
Neutrophil response (HI-N) (pretreatment, all patients)	
 At least 100% increase and an absolute increase $>0.5 \times 10^9/L$ (pretreatment, $<1.0 \times 10^9/L$) Increments of neutrophils also for patients with a pretreatment ANC of $>1.0 \times 10^9/L$ are to be reported
Progression or relapse after HI†	
At least 1 of the following:
 
 At least 50% decrement from maximum response levels in granulocytes or platelets Reduction in Hb by ≥ 1.5 g/dL Transfusion dependence

†Certain targeted therapies, for example, those inhibiting mutant IDH proteins, may cause a differentiation syndrome, that is, a transient increase in the percentage of bone marrow blasts and an absolute increase in blood blasts; in the setting of therapy with such compounds, an increase in blasts may not necessarily indicate PD.

b) IWG 2023 response criteria for HR-MDS

For secondary endpoint and MDS population only

RESPONSE	DEFINITION
Complete remission (CR)	
 BM: $<5\%$ myeloblasts*; dysplasia may persist PB: Hb ≥ 10 g/dL, platelets $\geq 100 \times 10^9/L$; neutrophils $\geq 1.0 \times 10^9/L$; blasts $0\%^\dagger$
CR equivalent*	
Patients with $<5\%$ BM blasts at baseline:
 
 BM: $<5\%$ myeloblasts*; dysplasia may persist PB: Hb ≥ 10 g/dL, platelets $\geq 100 \times 10^9/L$; neutrophils $\geq 1.0 \times 10^9/L$; blasts $0\%^\dagger$ Full cytogenetic clearance of baseline abnormalities (complete cytogenetic response)
Partial remission (PR)	
All CR criteria except:
 
 BM blasts decreased by $\geq 50\%$ over pretreatment but still $\geq 5\%$ Cellularity and morphology not relevant

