‡ A few panelists felt that mCR could still have a value, especially in bridging patients to allo-HSCT, and should therefore, still be reported. If mCR is reported, it should not be included in the ORR. Prolonged SD (≥16 weeks) might have limited benefit in patients with HR-MDS who are not candidates for allo-HSCT. However, SD is a function of time of stability, and in single-arm studies without a control arm, it is challenging to assess whether SD reflects more indolent MDS biology in some patients vs the impact of therapy. Furthermore, disease stability is included as part of the PFS definition. Therefore, SD should not be included in the ORR.

§ CRL and CRh are provisional entities that require additional prospective validation. Both CRL and CRh are included to allow prospective validation of their value in MDS. Similar to CR and PR, both are defined by blood counts at or around the time of response assessment and independently of the baseline blood counts. To be eligible for CRL, patients need to have achieved PB count levels at or around the time of assessment in 1 or 2 lineages, but not in all 3 lineages, that are at or above the CR threshold for the specific lineage(s). In patients with MDS/AML or MDS with increased blasts as defined by the 2022 International Consensus Classification and the 5th edition of WHO classification, respectively, reporting CRh defined as <5% blasts in the BM, 0% PB blasts, and partial recovery of PB counts (platelets ≥50 × 10⁹/L and ANC ≥0.5 × 10⁹/L) can be considered to achieve consistency with ELN 2022 AML response criteria. Similar to CRL, CRh is considered a provisional response category in MDS and requires additional prospective validation. If patients meet criteria for both CRL and CRh, they should be reported as having achieved CRL for the ORR as it represents a higher threshold for hematologic improvement.

|| For screening period and time window for assessment of transfusion dependency/independence, refer to Table 5 in the publication on the criteria (Zeidan et al., 2023)

¶ If cytogenetic analyses fail, repeating cytogenetics during a subsequent response assessment is recommended. MRD assessment in MDS is insufficiently validated at this time as a surrogate for OS. MRD-negative response can be reported as a provisional response category, and clinical trial protocols should predefine what techniques are used to detect MRD and what cutoffs are considered to define an MRD response.

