### 6.2.3 Other Endpoints

Endpoint

Vital signs
 
 
• Height (in cm)
 
• Weight (in kg)
 
• BMI (in kg/m^2)
 
• Systolic blood pressure [SBP] (in mmHg)
 
• Diastolic blood pressure [DBP] (in mmHg)
 
• Pulse rate (in beats/min)
 
• Respiratory rate (breaths/min)
 
• Body temperature (in °C)
 
 
Physical examination (Normal/ Abnormal, nCS/ Abnormal, CS) for each body system
 
 
• General appearance
 
• Head – Eyes – Ears – Neck – Throat
 
• Skin
 
• Musculoskeletal system
 
• Lymph nodes
 
• Nervous system
 
• Chest
 
• Abdomen
 
• Spine and limbs
 
 
Laboratory parameters:
 
 
• Serum chemistry
 

- Sodium (in mmol/L)
- Potassium (in mmol/L)
- Chloride (in mmol/L)
- Bicarbonate (if available) (in mmol/L)
- Calcium (in mmol/L)
- Magnesium (in mmol/L)
- Phosphate (in mmol/L)
- Urea nitrogen (in mmol/L)
- Creatinine (in mmol/L)
- Glomerular Filtration Rate, Estimated (in ml/min/1.73 m^2)
- Glucose (in mmol/L)
- Albumin (in mmol/L)
- Protein (in g/L)
- Alkaline phosphatase (in nkat/L)
- Bilirubin (in mmol/L)
- Aspartate Aminotransferase (in nkat/L)
- Alanine Aminotransferase (in nkat/L)
- Urate (in mmol/L)
- Gamma Glutamyl Transferase (in mmol/L)
- Automated complete blood count
  - Erythrocytes (T/L)
  - Leukocytes (in G/L)
  - Neutrophils (in 10^9/L)
  - Eosinophils (in G/L)
  - Basophils (in G/L)
  - Lymphocytes (in G/L)
  - Monocytes (in G/L)

- Haemoglobin (in g/dL)
- Haematocrit (in %)
- Nucleated Erythrocytes (in T/L)
- Reticulocytes (in T/L)
- Platelets ( $10^9/L$ )
- Ery. Mean Corpuscular Volume (in fL)
- Ery. Mean Corpuscular Hemoglobin (in fmol)
- Ery. Mean Corpuscular HGB Concentration (in mmol/L)
- Erythrocytes Distribution Width (in %)
- Cytogenetic Analysis
  - Number of metaphases available for analysis (<20 or  $\geq 20$ )
  - Karyotype (according to IPSS-R-Score: very good, good, intermediate, poor, very poor))
- BM Cytology Assessment
  - Blasts in Bone Marrow (in %)
  - Auer Rods (in %, not detectable is set to 0%)
  - Ringed Sideroblasts (in %, not detectable is set to 0%)
  - Dysplasia (>10% Dysplasia in Erythropoiesis (yes/no), >10% Dysplasia in Thrombopoiesis (yes/no), >10% Dysplasia in Granulopoiesis (yes/no))
- CBC with differential:

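### Protocol 8.1.5 requires visit 9 cytogenetics for the primary endpoint although its criteria never use karyotype, so a failed karyotype can be handled differently from site to site

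*Protocol*

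**What the plan says.** **What must be available.** Protocol 8.1.5 covers the disease assessment that yields the primary endpoint. Its minimum data set starts with marrow morphology and automated blood counts. For the remaining items it says: "cytogenetic results of visit 9 as well as any information on Hb and transfusions between enrollment and visit 9 are required". It adds that all of these "must be available prior to / for the disease assessment". It makes no exception for a karyotype that fails or was never obtained.

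**What the endpoint is built from.** Protocol 2.3.1 and SAP 7.7.4 define a responder as a patient with CR, CRi, PR or hematologic improvement under the combined criteria in Appendix III a) (SAP Appendix 2 a)). Complete remission, for example, needs a marrow blast percentage below 5%, "absence of circulating blasts and blasts with Auer rods; absence of extramedullary disease", and neutrophil and platelet thresholds.

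**What happens when response is unknown.** Protocol 2.3.1: "Patients for whom the overall hematologic response cannot be determined will be considered as treatment failures". SAP 7.7.4 repeats the rule.

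**What is said about failed cytogenetics.** The only text is a footnote to the IWG 2023 criteria in Appendix III b), which serve a secondary endpoint in MDS patients: "If cytogenetic analyses fail, repeating cytogenetics during a subsequent response assessment is recommended".

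**Which variable is analysed.** SAP 6.2.1 bases the main analysis on the investigator's responder item in the eCRF (RS_DSRESP).

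**The concern.** A required input that the endpoint definition does not use cannot improve the classification. It can only hold the classification up or prevent it. With the rule that an undetermined response is a failure, any loss goes one way: a responder may be recorded as a failure, but a non-responder cannot become a responder.

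The protocol does not tell a site what to do when marrow morphology, counts and transfusion records are complete and only the karyotype is absent. One investigator may take 8.1.5 at its word and leave the assessment incomplete. Another may apply Appendix III a) and tick the responder item. The recorded endpoint would then depend on how the site read a data-availability sentence.

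The per-protocol analysis is exposed as well, because SAP 7.3 gives an assessment of the primary endpoint that was not performed as an example of a critical deviation. The response rate is estimated separately for each dosing cohort, so a single reclassified patient is visible in the result.

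**Working it through.** **Step 1. Does any primary category need a karyotype?** Appendix III a), category by category:

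| Category | Inputs | Karyotype? |
|---|---|---|
| CR, CRi | marrow and blood blasts, Auer rods, extramedullary disease, ANC, platelets | no |
| PR | hematologic CR criteria, change in marrow blasts | no |
| MLFS | marrow blasts, Auer rods, extramedullary disease | no |
| SD | exclusion of the other categories | no |
| PD, relapse | marrow and blood blasts, ANC, platelets, extramedullary disease | no |
| HI-E | Hb, RBC transfusions | no |
| HI-P, HI-N | platelets (with bleeding symptoms), neutrophils | no |
| Loss of HI | counts, Hb, transfusions | no |

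**Step 2. Is the requirement repeated elsewhere?** Protocol 5.1.3 describes the same assessment through marrow and blood samples, blood counts and cytomorphology, and names no cytogenetics. Protocol 8.1.4 applies the same criteria after cycle 2 with local cytomorphology and sets no cytogenetic precondition. Protocol 8.2.4 does list cytogenetic analysis among the elements of response assessment, but gives cytogenetic response as the purpose of the testing.

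**Step 3. Where is karyotype used?** Only in Appendix III b), in two places. The first is the CR-equivalent category, which is for patients with under 5% marrow blasts at baseline. Inclusion criterion 8 requires at least 5% "bone marrow blasts at screening", so it should not arise in eligible patients. The second is a separate cytogenetic response row, which is secondary, MDS only and not part of the IWG 2023 ORR.

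**Step 4. Illustrative size.** The plan has no figure on this point to reproduce. Inputs:

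- True response rate 0.20, the expected rate in protocol 10.3, used for illustration only.
- 20 patients, also from 10.3, because current cohort sizes are blacked out.
- f = share of visit 9 karyotypes permanently unusable. This is not in the documents; the range 5% to 20% is assumed, independent of response.
- g = share of those cases that end up scored as non-response. This is unknown, from 0 (all sites classify from the other data) to 1 (all read 8.1.5 literally).

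Recorded rate = 0.20 × (1 − f × g). With g = 1:

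| f | Recorded rate | Expected responders lost, 20 × 0.20 × f | P(at least one lost), 1 − (1 − 0.20f)^20 |
|---|---|---|---|
| 5% | 0.19 | 0.2 | 18% |
| 10% | 0.18 | 0.4 | 33% |
| 15% | 0.17 | 0.6 | 46% |
| 20% | 0.16 | 0.8 | 56% |

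With g = 0.5 and f = 10%, the recorded rate is 0.20 × (1 − 0.05) = 0.19. With g = 0 nothing is lost.

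One responder lost in 20, from 4 to 3, moves the estimate from 20% (exact 90% CI 7.1% to 40.1%) to 15% (4.2% to 34.4%).

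**The case against.** The strongest reply is that the harm does not follow from the text. Protocol 2.3.1 counts a failure only when response cannot be determined. If Appendix III a) needs no karyotype, a patient with complete marrow, count and transfusion data can be determined, and SAP 7.7.4 classifies as a responder anyone who meets a criterion. The main analysis takes the investigator's own entry. This largely stands: no sentence says that a missing karyotype makes response undeterminable. What it leaves is an unqualified requirement in 8.1.5 that points the other way, and no rule to settle the conflict.

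The reply on late results stands in full. The schedule footnote on response assessment keeps the assessment open until the necessary laboratory results arrive, and 8.1.5 deals separately with the timing of the first extension dose. A pending karyotype delays the classification and does not by itself create a failure. Only a permanently failed or missing result matters.

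A reader might also infer that the SAP expects failures because it records "Number of metaphases available for analysis" as below 20 or at least 20. The SAP does not call a count below 20 failed or unusable, so this is no evidence of a failure rate.

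A reader might infer that cytogenetics serve no response category at all. That holds for the primary criteria only; the IWG 2023 cytogenetic response does use them.

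Finally, protocol 10.1 makes all analyses exploratory, and the SAP document history reports no responders in the interim data. No test decision is at risk, and the interim data show no responder who was lost in this way.

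**Conclusion.** The point holds as a conflict between sections with a possible one-way effect; its severity is minor to moderate. Section 8.1.5 makes mandatory an input that the primary criteria do not use and that 5.1.3 omits. Where the karyotype permanently fails or is missing, sites may classify like patients differently, and the rule for undetermined response would then push the recorded rate down.

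The size is unknown. The range of 19% to 16% in place of 20% rests on an assumed failure rate of 5% to 20%, independence from response, and every such case being scored as non-response. For a given failure rate that last assumption is the worst case.

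A reader might go further and conclude that the plan turns responders into failures whenever a karyotype is lost, or that the loss differs by site or cohort. The documents do not support either. The first would need a rule linking karyotype to determinability, and none exists. For the second, the documents give no data on laboratory performance, and protocol 8.1.1 calls for standardized local analysis and reporting.

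**What to change.** 1. **Protocol 8.1.5.** Remove cytogenetic results from the data required for the primary assessment under Appendix III a). Keep cytomorphology, automated CBC, and the Hb and transfusion record.
2. **Protocol 8.1.5 and SAP 7.7.4.** Add one sentence: a failed, missing or pending karyotype does not make the hematologic response undeterminable.
3. **Protocol 8.2.4.** Clarify only that cytogenetics serve the assessment of cytogenetic response and not the primary responder classification.
4. **Leave unchanged** the visit 9 cytogenetic sampling, Listing 16.9.6 and the use of cytogenetics for the IWG 2023 cytogenetic response.

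The cost is a few sentences. Sampling is unchanged, so no data are lost. If a protocol amendment for this alone is not worthwhile, the SAP sentence can go into an update before database lock, which SAP 2.10 allows for non-substantial changes, with the same guidance sent to sites. At the data review meeting, list every FAS patient whose response is undetermined and give the reason. That would show whether any case arose from karyotype alone and would replace the assumed range with a count.
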